12.2 ADVERSE EVENT CHARACTERISTICS

CTCAE term (AE description) and grade: The descriptions and grading scales found in the revised NCI Common Terminology Criteria for Adverse Events (CTCAE) version 4.0 will be utilized for AE reporting. All appropriate treatment areas should have access to a copy of the CTCAE version 4.0. A copy of the CTCAE version 4.0 can be downloaded from the CTEP web site http://ctep.cancer.gov/protocolDevelopment/electronic applications/ctc.htm.

'Expectedness': AEs can be 'Unexpected' or 'Expected' for expedited reporting purposes only. Expected AEs are defined as those described in the ublituximab Investigator Brochure. Please refer to the ibrutinib prescribing information for a listing of expected AEs.

12.3 DEFINITIONS OF ADVERSE EVENTS

An adverse event (AE) is any untoward medical occurrence in a patient or clinical investigation patient administered a pharmaceutical product. An AE does not necessarily have to have a causal relationship with this treatment. An adverse event (AE) can therefore be any unfavorable and unintended sign (including an abnormal laboratory finding, for example), symptom, or disease temporarily associated with the use of a medicinal product, whether or not considered related to the medicinal product. This includes any occurrence that is new in onset or aggravated in severity or frequency from the baseline condition.

In clinical studies, an AE can include an undesirable medical condition occurring at any time, including run-in or washout periods, even if no study treatment has been administered. The NCI Common Terminology Criteria for Adverse Events (CTCAE) v4.0 is to be used for the grading of severity of symptoms and abnormal findings. For adverse events not covered by the NCI-CTCAE Version 4.0 grading system, the following definitions will be used:

- **Grade 1**: Mild; asymptomatic or mild symptoms; clinical or diagnostic observations only; intervention not indicated.
- **Grade 2:** Moderate; minimal, local or non-invasive intervention indicated.
- **Grade 3**: Severe or medically significant but not immediately life-threatening; hospitalization or prolongation of hospitalization indicated.
- **Grade 4**: Life-threatening consequences; urgent intervention indicated.

UTX-IB-301

• **Grade 5**: Death related to AE.

12.4 ADVERSE EVENTS (AE'S) AND TREATMENT EMERGENT ADVERSE EVENTS (TEAE'S)

All AEs and SAEs occurring on study will be listed by patient. The frequency and percentages of patients with treatment-emergent adverse events (TEAEs) will be tabulated by system organ class (SOC) and preferred term (PT), where treatment-emergent is defined as any AE that:

- Occurs after first dosing of study medication and through the end of the study or up through 30 days after the last dose of study treatment, or
- Is considered treatment-related regardless of the start date of the event, or
- Is present before first dosing of study medication but worsens in intensity or the investigator subsequently considers treatment-related.

TEAEs that are considered at least possibly related to study treatment will be tabulated as well as deaths, SAEs, and events resulting in treatment discontinuation.

AEs that occur after informed consent but before first dosing of study medication will not be summarized but will be listed.

At each level of summarization, a patient will be counted only once for each AE, SOC, or PT experienced within that level. In the summation for AE severity, within each level of AE, SOC, or PT experienced, the one with the highest severity will be included. In the summation for AE's relationship to the study drug, within each level of AE, SOC, or PT experienced, the one with the closest relationship to the study drug will be included.

12.5 ADVERSE EVENTS/SERIOUS ADVERSE EVENT CAUSALITY ASSESSMENT

The Investigator must also assess the relationship of any adverse event to the use of study drugs (whether none, one, or both), based on available information, using the following guidelines:

- **Not Related**: Clear-cut temporal and/or mechanistic relation to a cause other than the study drug(s).
- **Doubtful**: There is no reasonable possibility that the event is related to the study drug(s) but a definite cause cannot be ascertained.
- **Possible**: There is still a reasonable possibility that the cause of the event was the study drug(s) but there exists a more likely cause of the event such as complications of progressive disease.
- **Probable**: The most likely cause of the event is the study drug(s) but other causes cannot be completely excluded.
- **Definite:** Clear cut temporal and/or mechanistic relation to the study drug(s). All other causes have been eliminated. Events classified as definite will often be confirmed by documenting resolution on discontinuation of the study drug and recurrence upon resumption.

UTX-IB-301

12.5.1 RECORDING OF ADVERSE EVENTS

All adverse events of any patient during the course of the study will be reported on the case report form, and the investigator will give his or her opinion as to the relationship of the adverse event to study drug treatment (i.e., whether the event is related or unrelated to study drug administration – either ublituximab and/or ibrutinib). If the adverse event is serious, it should be reported as soon as possible and no greater than 24 hours to the sponsor or designee. Other untoward events occurring in the framework of a clinical study are also to be recorded as AEs (i.e., AEs that occur prior to assignment of study treatment that are related to a protocol-mandated intervention, including invasive procedures such as biopsies, medication washout, or no treatment run-in).

All AEs regardless of seriousness or relationship to ublituximab or ibrutinib treatment spanning from Cycle 1/Day 1 until 30 calendar days after discontinuation or completion of either protocol-specific treatment as defined by the protocol for that patient, are to be recorded on the eCRF.

12.5.2 ABNORMAL LABORATORY VALUES AND VITAL SIGNS

The reporting of abnormalities of vital signs as adverse events should be avoided. Abnormalities of vital signs should not be reported unless any criterion for an SAE is fulfilled, the vital signs abnormalities cause the patient to discontinue study treatment, or the investigator insists that the abnormality should be reported as an AE. Abnormal laboratory results should be noted in the eCRF as an adverse event if they are associated with an overdose, require or prolong inpatient hospitalization, or are otherwise considered clinically significant by the investigator. If an abnormal laboratory value or vital sign is associated with clinical signs and/or symptoms, the sign or symptom should be reported as an AE, and the associated laboratory value or vital sign should be considered additional information that must be collected in the relevant eCRF. If the laboratory abnormality is a sign of a disease or syndrome, only the diagnosis needs to be recorded on the SAE Report Form or AE eCRF.

Clinical Laboratory Results will be summarized. Summary statistics for actual values and for changes from baseline will be tabulated for laboratory results by scheduled visit. Patients with laboratory values outside of the normal reference range at any post-baseline assessment will be summarized, and graded per NCI CTCAE Version 4.0 when applicable. Patient incidence of abnormal laboratory results will be summarized by treatment group and maximum grade for each abnormal laboratory finding.

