8.2.1 GUIDELINES FOR ADMINISTRATION OF UBLITUXIMAB

- *Method of Administration:* Ublituximab will be administered as an intravenous infusion through a dedicated line.
- Potential Drug Interactions: No Drug Interactions have been reported to date.
- Pre-medications: Pre-medicate approximately 30 minutes prior to each dose of ublituximab
 with an antihistamine (diphenhydramine 50 mg or equivalent), and a corticosteroid
 (dexamethasone 10-20 mg or equivalent). Use of corticosteroids as a premedication after
 cycle 6 is at the discretion of the investigator.
 - Use of oral acetaminophen should be restricted to patients who experience fever or pyrexia after week 1 dose, or as clinically warranted.

UTX-IB-301

- *Hypersensitivity and Infusion Reaction Precautions*: Medication and resuscitation equipment must be available per institutional guidelines prior to ublituximab administration for the emergency management of potential anaphylactic reactions.
- Patient Care Implications:
 - o Ublituximab should not be administered as an IV push or bolus.
 - o Ublituximab should only be diluted in 0.9% NaCl.
 - Diluted ublituximab should be checked before administration for cloudiness, color, or deposits. Ublituximab should not be administered if does not conform to the specifications. Immediately inform the Monitor/Sponsor with any product quality concerns or questions.
 - o It is recommended that ublituximab be administered immediately after dilution.
 - No other treatment may be co-administered with ublituximab (other than for immediate intervention for adverse event).
 - o Concurrent glucocorticoid therapy as long as started for at least 7 days prior to study entry (≤ 10 mg per day of prednisone or equivalent) is allowed as clinically warranted.
 - Since infusion-related hypotension may occur, antihypertensive medications should be withheld 24 hours prior to and throughout infusion of ublituximab
 - For patients at risk for tumor lysis syndrome in the opinion of the treating investigator, prophylaxis with allopurinol or per recommended institutional standards should be considered.

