Atrial fibrillation and atrial flutter (range, 6 to 9%) have occurred in patients treated with ibrutinib, particularly in patients with cardiac risk factors, hypertension, acute infections, and a previous history of atrial fibrillation. Periodically monitor patients clinically for atrial fibrillation. Patients who develop arrhythmic symptoms (e.g., palpitations, lightheadedness) or new onset dyspnea should have an ECG performed. If atrial fibrillation persists, consider the risks and benefits of ibrutinib treatment and dose modification in the prescribing information.

Hypertension

Hypertension (range, 6 to 17%) has occurred in patients treated with ibrutinib with a median time to onset of 4.6 months (range, 0.03 to 22 months). Monitor patients for new onset hypertension or hypertension that is not adequately controlled after starting ibrutinib. Adjust existing antihypertensive medications and/or initiate anti-hypertensive treatment as appropriate.

Second Primary Malignancies

Other malignancies (range, 3 to 16%) including non-skin carcinomas (range, 1 to 4%) have occurred in patients treated with ibrutinib. The most frequent second primary malignancy was non-melanoma skin cancer (range, 2 to 13%).

Tumor Lysis Syndrome

UTX-IB-301

Tumor lysis syndrome has been infrequently reported with ibrutinib therapy. Assess the baseline risk (e.g., high tumor burden) and take appropriate precautions. Monitor patients closely and treat as appropriate.

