8.1.2 STATISTICAL ANALYSIS

Continuous laboratory test results will be summarized descriptively by study drug received for actual values and for changes from Cycle 1 Day 1. Visits to be summarized include all scheduled post-Cycle 1 Day 1 visits.

Shift from baseline tables for laboratory parameters will be presented. Categories will be based on CTCAE grade (where applicable) or by high/low flags (where CTCAE grades are not defined). Data will be analyzed at all post-Cycle 1 Day 1 visits, by worst grade post-Cycle 1 Day 1. Laboratory tests that have high and low abnormalities will be summarized separately for each direction (e.g., hypocalcemia and hypercalcemia).

Abnormalities in laboratory tests that the investigator considers clinically significant will be recorded and summarized as AEs.

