8.2.2 STATISTICAL ANALYSIS

Summary tables of vital signs and change from baseline will be presented for all scheduled visits where vital signs were assessed. All recorded vital sign data will be listed.

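### Protocol 12.5.2 steers sites away from reporting abnormal vital signs as AEs, in conflict with other sections, so non-serious hypertension is likely to be under-recorded in both arms by an unknown amount

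*Protocol*

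**What the plan says.** Protocol 12.5.2 opens its vital-sign rule with a default: "The reporting of abnormalities of vital signs as adverse events should be avoided". It continues: "Abnormalities of vital signs should not be reported unless any criterion for an SAE is fulfilled". Two further exceptions follow: "the vital signs abnormalities cause the patient to discontinue study treatment", or "the investigator insists that the abnormality should be reported as an AE".

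The same section treats laboratory results more openly. They are AEs if linked to overdose or hospitalization, or if the investigator otherwise finds them clinically significant. SAP 8.1.2 repeats this: "Abnormalities in laboratory tests that the investigator considers clinically significant will be recorded and summarized as AEs". SAP 8.2.2 has no matching sentence for vital signs.

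Where an abnormal vital sign comes with symptoms, 12.5.2 makes the symptom the AE and keeps the reading as supporting information on the eCRF. The sentence that lets a diagnosis replace its signs refers only to laboratory abnormalities.

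On the risk itself, Protocol 9.2.1.1 states: "Hypertension (range, 6 to 17%) has occurred in patients treated with ibrutinib with a median time to onset of 4.6 months". It asks sites to monitor for new or poorly controlled hypertension and to treat it. Protocol 9.1.1.3 lists hypertension for single-agent ublituximab in the band from 5% to below 10%.

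On BP data, SAP 8.2.2 says: "Summary tables of vital signs and change from baseline will be presented for all scheduled visits where vital signs were assessed". Protocol 8.2.1 says that "antihypertensive medications should be withheld 24 hours prior to and throughout infusion of ublituximab". Only Arm A receives ublituximab.

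**The concern.** TEAE tables are built from terms recorded on the case report form (SAP 8). An event that sites are told not to record cannot appear in them. A patient with new, asymptomatic hypertension who is treated and stays on study drug meets neither of the first two exceptions in 12.5.2. That leaves insistence by the investigator, which overrides a default and is not a criterion.

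At stake is the reported incidence of a known risk of the drug given in both arms. Consistency is also at stake: two sites could handle the same event differently, and each could point to a protocol section in support. If the AE tables are weak here, a reader turns to the BP summaries, so it matters whether those can carry the weight.

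**Working it through.** The documents give no planned figure for hypertension or BP, and SAP 7 makes any formal safety comparison post-hoc. There is nothing to reproduce. The check is a comparison of sections plus simple arithmetic.

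**1. Sections side by side**

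| Section | What it implies for new, non-serious hypertension |
|---|---|
| Protocol 12.5.2 | Not reported by default; three exceptions |
| Protocol 12.3 | An unfavorable sign, new or aggravated, is an AE |
| Protocol 12.5.1 | All AEs are recorded, serious or not |
| Protocol 12.9 | A recognized condition is named in place of its signs and symptoms |
| Protocol 12.9.5 | A worsened pre-existing condition is an AE |
| Protocol 12.1, SAP 7 | Safety rests partly on clinically significant vital-sign changes |
| Protocol 9.2.1.1 | Hypertension is a named risk; monitor and treat |

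The first row conflicts with the others, and no section says which prevails.

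**2. Expected cases per arm**

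About 120 patients randomized 1:1 (SAP 3.6) gives about 60 per arm. Applying the ibrutinib range to this trial is an assumption.

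- 60 × 0.06 = 3.6
- 60 × 0.17 = 10.2

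**3. What partial recording would do**

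The capture fraction c is an assumption, since the documents give none. Expected recorded cases = 60 × rate × c. The chance that an arm shows none = (1 − rate × c)^60.

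| c | Recorded at 6% | Chance of none at 6% | Recorded at 17% | Chance of none at 17% |
|---|---|---|---|---|
| 100% | 3.6 | 2.4% | 10.2 | <0.1% |
| 75% | 2.7 | 6.3% | 7.7 | <0.1% |
| 50% | 1.8 | 16.1% | 5.1 | 0.5% |
| 25% | 0.9 | 40.4% | 2.6 | 7.4% |

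This shows sensitivity to c. It does not estimate the shortfall.

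**4. BP visits against infusion visits (Protocol Table 2)**

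Through Cycle 12, Arm A has these scheduled on-treatment BP visits: Cycle 1 Days 1, 2, 8 and 15 (4); Day 1 of Cycles 2 to 6 (5); Day 1 of Cycles 9 and 12 (2). That is 4 + 5 + 2 = 11, and all 11 are ublituximab dosing visits. Arm B shares 10 of them, since Day 2 is for Arm A only, and has no hold. Table 2 requires hematology before infusion but sets no such rule for BP.

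The consequence depends on the patient:

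- Already on antihypertensives, Arm A, baseline at Cycle 1 Day 1 (allowed by SAP 4.1): both readings fall under the hold, so the change is like with like.
- Same patient, baseline at screening: baseline is not under the hold and later readings are.
- Antihypertensive started on study: later readings fall under the hold in Arm A and on drug in Arm B.
- Actual values in any treated patient: the two arms are measured under different conditions.

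**5. Timing, assuming no delays and 30.4 days per month**

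- Last BP visit on the 28-day schedule, Cycle 6 Day 1: 5 × 28 = 140 days; 140 / 30.4 = 4.6 months, equal to the stated median onset.
- Next visit, Cycle 9 Day 1: 8 × 28 = 224 days; 224 / 30.4 = 7.4 months, with a window of ±14 days.

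If onset here follows that median, about half of onsets come after BP visits have thinned to every 84 days.

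**The case against.** The strongest reply is that 12.5.2 restricts measurements, while hypertension is a condition. Protocol 9.1.1.3 itself lists it under vascular disorders. Sections 12.3, 12.5.1, 12.9 and 12.9.5 give a site good grounds to record it. This stands in part: it rules out saying that cases will be missed as a matter of course. It does not remove the conflict, because 12.5.2 is the specific rule and its diagnosis sentence leaves vital signs out.

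A reader might also draw stronger conclusions that the documents do not support:

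- *Most cases are missed.* No capture rate is given, and 3.6 to 10.2 are expected cases, not missed ones.
- *The rule biases the arm comparison.* It is the same in both arms, and both receive ibrutinib. Its main effect is on absolute incidence.
- *The ibrutinib interruption rule loses its trigger.* Protocol 8.4 requires CTCAE toxicity assessment at each visit, and 8.4.2 acts on the toxicity, not on an AE entry.
- *Only the BP summary remains.* SAP 8.2.2 also lists every recorded vital sign, and SAP 5.6 tabulates concomitant medications by class. These help, but listings are not an incidence analysis, and the concomitant table mixes drugs continued from before first dose with new ones.
- *A mandated hold distorts Arm A upward.* The text says should, and it affects only patients on antihypertensives. Baseline may fall under the hold too, and visit windows of ±3 to ±14 days can separate a reading from an infusion. Protocol 8.2.1 also cites infusion-related hypotension, so the direction is open.

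**Conclusion.** The point holds in a limited form and is worth correcting. Protocol 12.5.2 sets a default against recording abnormal vital signs that conflicts with the protocol's AE definition, its recording rules and its stated basis for safety evaluation. Non-serious, asymptomatic hypertension is likely to be under-recorded and inconsistently recorded in the TEAE tables of both arms. About 4 to 10 cases per arm would be expected, assuming 60 patients per arm and the 6 to 17% range. The number lost cannot be computed.

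The by-visit BP summaries only partly fill the gap. Actual values, and changes in patients who start antihypertensives on study, may not be comparable between arms, in an unknown direction. Readings also become sparse from about the stated median onset. The primary endpoint is unaffected, and no view is taken on the antihypertensive hold.

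**What to change.** **Protocol 12.5.2.** Reconcile it with 12.3 and 12.9 by applying the existing laboratory standard to vital signs: record an abnormality as an AE when the investigator considers it clinically significant. Extend the diagnosis sentence to vital signs, so that the condition, such as hypertension, is recorded when there is one.

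**SAP 8.2.2.** Add two tables by arm:

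- BP by CTCAE grade or as shift from baseline, as SAP 8.1.2 already provides for laboratory tests;
- antihypertensives newly started after first dose.

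Add a note that mean BP at infusion visits is not a clean between-arm comparison.

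**Optional.** Record on the eCRF the time of BP relative to infusion and whether antihypertensives were withheld.

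**Cost.** A wording change, two tables and more non-serious AE records. Both tables use data already collected, so they help even where a protocol change comes too late for events already handled under 12.5.2. The optional item needs new eCRF fields.

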12.5.3 HANDLING OF ADVERSE EVENTS

All adverse events resulting in discontinuation from the study should be followed until resolution or stabilization. Patients should be followed for AEs for 30 calendar days after discontinuation or completion of protocol-specific treatment (either ublituximab or ibrutinib). All new AEs occurring during this period must be reported and followed until resolution unless, in the opinion of the investigator, these values are not likely to improve because of the underlying disease. In this case, the investigators must record his or her reasoning for this decision in the patient's medical record and as a comment on the eCRF. After 30 days, only AEs, SAEs, or deaths assessed by the investigator as treatment related are to be reported.

UTX-IB-301

12.6.1 DEFINITIONS OF SERIOUS ADVERSE EVENTS

The definitions of serious adverse events (SAEs) are given below. The investigator is responsible for ensuring that all staff involved in the study are familiar with the content of this section.

An SAE or reaction is defined as any untoward medical occurrence that:

- results in death, is immediately life-threatening,
- requires at least a 24-hour in-patient hospitalization or prolongation of existing hospitalization,
- results in persistent or significant disability/incapacity, and/or
- causes a congenital anomaly/birth defect.

Medical and scientific judgment should be exercised in deciding whether expedited reporting is appropriate in other situations, such as important medical events that may not be immediately life-threatening or result in death or hospitalization, but may jeopardize the patient or may require intervention to prevent one of the other outcomes listed in the previous definition. These should also usually be considered serious. Examples of such events are intensive treatment in an emergency room or at home for allergic bronchospasm; blood dyscrasias or convulsions that do not result in hospitalization; or development of drug dependency or drug abuse.

Progression of malignancy (including fatal outcomes), if documented by use of appropriate method (for example, as per IWCLL Hallek et al. 2008, should not be reported as a serious adverse event.

A suspected unexpected serious adverse reaction (SUSAR) is defined as an SAE that is suspected to be at least possibly related to study medication(s) and is an unexpected event. SUSAR reporting is encompassed within SAE reporting guidelines as defined in this section.

Treatment within or admission to the following facilities is not considered to meet the criteria of "inpatient hospitalization" (although if any other SAE criteria are met, the event must still be treated as an SAE and immediately reported):

- Emergency Department or Emergency Room
- Outpatient or same-day surgery units
- Observation or short-stay unit
- Rehabilitation facility
- Hospice or skilled nursing facility
- Nursing homes, Custodial care or Respite care facility

Hospitalization during the study for a pre-planned surgical or medical procedure (one which was planned prior to entry in the study), does not require reporting as a serious adverse event to the Sponsor.

UTX-IB-301

